8.2. Echocardiography

A summary table of observed and change from baseline values in numerical echocardiography results will be provided at each scheduled visit.

A by-subject listing will be presented for each ECHO parameter, including LVMi measurement, and other cardiac parameters, such as ejection fraction, fractional shortening, left ventricular internal diameter end diastole and end systole, midwall fractional shortening, and wall thickness.

8.3. Subject Questionnaires

8.3.1. Electronic Diary (FABPRO-GI and Pain Questionnaire for Clinical Trials [24-hour version])

Subjects are asked to complete daily diary entries at approximately the same time of day (preferably in the evening before bed time) beginning on Day 1 and for the duration of the study. Diary entries will include completion of the short FABPRO-GI and Pain Questionnaire.

The FABPRO-GI and Pain Questionnaire for Clinical Trials (24-hour version) consists of 4 questions regarding gastrointestinal signs and symptoms and 2 questions regarding pain relative to the past 24 hours. Subjects will record the frequency and consistency of stools using the Bristol Stool Scale, a pictorial chart and descriptive text for 7 types of stool, ranging from Type 1 (separate hard lumps, like nuts – hard to pass) through Type 7 (watery, no solid pieces – entirely liquid). Subjects will also rate the severity of their worst occurrence of diarrhea, constipation, tummy pain, and overall pain from 0 (none) to 10 (worst possible); for tummy pain, subjects will indicate the location of any tummy pain using a diagram.

Descriptive summary tables will be provided for observed monthly average scores of e-diary responses for FABPRO-GI and Pain Questionnaires for Clinical Trials (24-hour version) by subgroup, ie, sex (male, female), ERT status (ERT naïve, ERT experienced), and overall if feasible.

e-diary responses will include:

- Monthly average of worst tummy pain in past 24 hours score based on the tummy pain question in the FABPRO-GI and Pain Questionnaire for Clinical Trials (24-hour version) with its 0 to 10 scale (0 = no pain, 10 = worst possible pain)
- Monthly average of overall pain in past 24 hours score in the (FABPRO-GI and Pain Questionnaire for Clinical Trials (24-hour version) with its 0 to 10 scale (0 = no pain, 10 = worst possible pain)
- 3) Monthly average of daily ratings of severity will be assessed separately for each of the following items: diarrhea and constipation.

Visit mapping:

FABPRO-GI and Pain questionnaires are assessed daily. For each subject, there are scheduled visits at Month 1, 3, 6, 9 and 12/ET. The closest date to the date of the scheduled visits are mapped to the corresponding visits. If there are multiple dates at the same distance to the scheduled date, the later date will be assigned to the scheduled visit.

Monthly averaged scores:

The monthly average score is calculated as the sum of the total scores of each test from 30 day prior to the scheduled dates of Month 1, 3, 6, 9 and 12/ET divided by the number of days when actual assessments were done. If there are more than 6 days of missing assessments, then the total score for the monthly scheduled visit is set as missing, since less than 80% assessments are available.

A by-subject listing of responses from FABPRO-GI and Pain Questionnaires for Clinical Trials (24-hour version) will be provided.

8.3.2. Patient Global Impression of Change

The PGI-C consists of 4 questions regarding diarrhea, abdominal (tummy) pain, overall pain, and daily living to be answered using a 7-point scale. Descriptive by visit summary tables at Month 3, 6 and 12/ET will be provided for observed PGI-C scores and average of overall Gastrointestinal (GI) symptoms scores. Categorical summary of improved and worsened status for each question at Month 3, 6 and 12/ET will also be summarized by visit and subgroup, ie, sex (male, female), ERT status (ERT naïve, ERT experienced), and overall if feasible. Improved status includes "Much better", "Better" and "A little better"; Worsened status includes "A little worse", "Worse" and "Much worse"; "The same" will be categorized separately.

A by-subject listing of PGI-C Questionnaires will be provided.

8.3.3. Fabry-Specific Pediatric Health and Pain Questionnaire

The FPHPQ includes questions about Fabry disease-specific symptoms (eg, sweating, pain, dizziness and tiredness, heat and cold intolerance, swollen eyelids, gastrointestinal symptoms, feeling thirsty, difficulty hearing, ringing or buzzing noise in the ears, and ability and enjoyment to participate in sports). The frequency of these symptoms will be rated using a 5-point Likert scale (0=Never, 1=Seldom, 2=Sometimes, 3=Often, 4=Always). Pain intensity is measured on an 11-point scale, numeric responses are given for onset of pain and school days missed, and yes/no questions are posed about difficulty hearing and other problems not specifically mentioned. There are 2 age-specific self-report versions for children 8 to 12 years and 13 to 18 years, respectively.

Descriptive summaries will be provided for the FPHPQ observed and change from baseline scores by visit and subgroup, ie, sex (male, female), ERT status (ERT naïve, ERT experienced), and overall if feasible. Unscheduled visits will not be included.

A by-subject listing of FPHPQ scores will be provided.

8.3.4. Pediatric Quality of Life Inventory

The PedsQL[™] is a modular approach to measuring health-related quality of life in healthy children and adolescents and those with acute and chronic health conditions. It consists of 23 items and includes questions about physical functioning (8 items), emotional functioning (5 items), social functioning (5 items), and school functioning (5 items) relative to the prior 7 days, using a 5-point scale (0=Never, 1=Seldom, 2=Sometimes, 3=Often, 4=Always). Both parents or legally-authorized representatives and subjects complete the appropriate version of the PedsQL[™] independently of one another. Parents or legally-authorized representatives and subjects may self-administer the questions after introductory instructions are given by study site personnel.

PedsQL[™] scoring procedure is as listed below:

Step 1: Transform Score:

Item scores are reversed and linearly transformed to a 0-100 scale as follows: 0=100, 1=75, 2=50, 3=25, 4=0.

Step 2: Calculate Scores:

Score by Dimensions:

If more than 50% of the items in the scale are missing, the scores should not be computed.

Mean score = Sum of the items over the number of items answered.

Psychosocial Health Summary Score = Sum of the items over the number of items answered in the Emotional, Social, and School Functioning Scales;

Physical Health Summary Score = Physical Functioning Score;

Total Score: Sum of all the items over the number of items answered on all the scales.

Descriptive summary tables will be provided for the PedsQL[™] observed and change from baseline of psychosocial, physical and total scores by visit and subgroup, ie, sex (male, female), ERT status (ERT naïve, ERT experienced), and overall if feasible.

A by-subject listing of PedsQL[™] scores for each single question as well as psychosocial, physical and total scores will be provided.

9. Analysis of Pharmacokinetics

Analysis of PK will be described in a separate PKAP.

10. Analysis of Pharmacodynamics

10.1. Primary PD Endpoint and Analysis

The PD endpoint is change in plasma levels of lyso-Gb₃. Descriptive summaries will be provided for the change from baseline to Month 3, Month 6, and Month 12/ET by sex (male and female), ERT status (ERT naïve, ERT experienced), and overall based on the safety population.

A by-subject listing will also be provided.

10.2. Other PD Analogs Analysis

Other PD endpoints are change in plasma levels of lyso-Gb₃ analogs. Descriptive summaries will be provided for the change from baseline to Month 3, Month 6, and Month 12/ET by sex (male and female), ERT status (ERT naïve, ERT experienced), and overall based on the safety population.

A by-subject listing will also be provided.

11. Safety

The analysis population used for safety analyses will be the safety population. Safety will be assessed on the basis of extent of exposure, incidence of TEAEs, SAEs and AEs leading to discontinuation, clinical laboratory data, vital signs including body weight and height, ECHO, ECG parameters, physical examinations, and tanner stage.

11.1. Extent of Exposure and Drug Compliance

The duration of study drug exposure (in days) and the number of doses of study drug exposure will be summarized for the safety population.

Average Dose Every Other Day is defined as:

Average Dose Every Other Day = [Total dose received/ (Duration of exposure + 1)] * 2

Drug Compliance is defined as:

Drug Compliance (%) = Average Dose Every Other Day/Planned Dose Every Other Day (ie, 150 mg)

Drug Compliance will be summarized using descriptive summaries. The number and percentage of subjects with Drug Compliance <80%, \geq 80% will be summarized.

A detailed listing of exposure to study drug and drug compliance will be presented.

11.2. Adverse Events

An overall summary of TEAEs, will be tabulated, including the number and percentage of subjects reporting:

- TEAEs
- Treatment-related TEAEs
- SAEs
- TEAEs leading to discontinuation of study drug
- TEAEs leading to death

The number of events and incidence rates will also be provided in the overall summary table. Incidence rate is calculated as: total events divided by the total patient years of exposure. Total patient years of exposure are the sum of the duration of exposure in years for all subjects.

Further, the following TEAE summaries will be provided by sex and overall:

- Any TEAEs by SOC and PT
- Any TEAEs by PT
- Treatment related TEAEs by SOC and PT
- TEAEs by intensity, by SOC and PT
- Serious TEAEs by SOC and PT
- Any non-serious TEAE by PT

The number and percentage of subjects reporting TEAEs will be tabulated by SOC and PT. Subjects are counted only once within each SOC and PT. TEAEs will be presented alphabetically by SOC and PT.

The number and percentage of subjects reporting TEAEs will also be tabulated by PT. Subjects are counted only once in each PT. TEAEs will be presented in the order of descending frequency in the overall group.

The number and percentage of subjects reporting TEAEs will be tabulated by SOC, PT and maximum severity. If a subject has more than one event within a given SOC or PT at different severities, the maximum severity will be tabulated. For example, if a subject had two events with the same preferred term, but one was moderate and the other severe, the severe TEAE will be included in the tabulation.

The number and percentage of subjects reporting treatment-related serious TEAEs will be tabulated by SOC and PT. Subjects are counted only once within each SOC and PT. Subject listings will also be provided for subjects with SAEs.

11.3. Laboratory Evaluations

Clinical laboratory test values (hematology, serum chemistry, and urinalysis) and changes from baseline will be summarized by each visit and subgroup, ie, sex (male, female), ERT status (ERT naïve, ERT experienced), and overall if feasible for the safety population. In addition, the following clinical summaries will be presented:

- The frequencies and percentages of potential clinically significant (PCS) abnormalities at any time;
- Tables displaying shifts from baseline to each assessment time-point in laboratory test values from normal to high or low using normal range including eGFR, urine protein, and albumin.

Potential clinically significant abnormalities will be determined both by investigator assessment or derivation from lab alert ranges provided by Amicus.

Clinically significant abnormal assessments for eGFR, urine protein and albumin will be summarized with frequency tables by sex (male, female), ERT status (ERT naïve, ERT experienced), and overall if feasible. Unscheduled visits will be included. Clinically significant abnormal values will be collected from investigator assessment on the CRF page.

By-subject safety laboratory listings will be generated incorporating information and assessment results obtained from the designated laboratory which provided normal range and reported out of range flags. All laboratory results in Système International (SI) units will be presented in data listings. Tests will be listed in alphabetical order within their respective panels (hematology, serum chemistry, and urinalysis).

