8.2.1. Inclusion Criteria

Subjects must meet all of the following criteria to be considered for enrollment in the study:

- 1. have a parent or legally-authorized representative who is willing and able to provide written informed consent and authorization for use and disclosure of personal health information or research-related health information, and subject provides assent, if applicable provides written informed consent
- 2. male or female, diagnosed with Fabry disease aged between 12 and < 18 years at baseline, and who might benefit from specific treatment for their condition, in the opinion of the investigator
- 3. confirmed, amenable *GLA* variant determined using the migalastat amenability assay

Note: For subjects without a known amenable *GLA* variant, *GLA* genotyping must be performed prior to Visit 2.

Note: For subjects with a *GLA* variant that has not yet been tested in the Migalastat Amenability Assay, amenability testing must be completed before Visit 2.

- 4. weight of \geq 45 kg (99 pounds) at screening
- 5. treatment-naïve or discontinued ERT treatment at least 14 days prior to screening
- 6. have at least one complication (ie, historical or current laboratory abnormality and/or sign/symptom) of Fabry disease, for example:
 - a. corneal whorls
 - b. neuropathic pain and/or acroparesthesia and/or acute crises persisting or recurring at least twice over the previous 3 months or longer, or; requiring management with analgesia
 - c. Fabry disease-related gastrointestinal signs and symptoms (eg, diarrhea, abdominal pain) persisting or recurring at least twice over the previous 3 months or longer
 - d. hypohidrosis (present for at least 3 months)
 - e. LVMi above the normal range for age and sex

- f. rhythm and/or conduction disturbances, for example:
 - episode of tachycardia or bradycardia,
 - arrhythmia, or;
 - abnormal PR, QRS, or QT interval
- g. reduced eGFR (using the Schwartz formula) for age and sex, or hyperfiltration (> 135 ml/min/1.73 m²)
- h. proteinuria or albuminuria in spot urine (early morning preferable) or as determined by the investigator (based on local laboratory results documented in the patient's medical record)
- i. plasma lyso-Gb₃ levels above normal (based on local laboratory results documented in the patient's medical record)
- j. hearing impairment and/or tinnitus
- 7. able to swallow capsules

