11.4. Vital Signs, Body Weight, and Height

Vital signs (blood pressure, pulse rate, respiratory rate, and oral temperature), height, and weight will be assessed at the scheduled visits specified in Section 4.6.

A summary table of observed and change from baseline values will be provided at each scheduled visit for the safety population, from baseline at Day 1-15, Month 1, Month 3, Month 6, Month 9 and Month 12/ET. Clinically significant abnormal results, in which unscheduled visits will be included, will be summarized with the frequency tables by sex (male, female), ERT status (ERT naïve, ERT experienced), and overall if feasible.

A by-subject listing will be provided for each vital sign parameter.

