11.5. Echocardiography

For categorical echocardiography results, an observed summary table will be provided by each parameter and visit in safety population. Scheduled visits will be included for by-visit summary tables.

Clinically significant abnormal assessments for each parameter will be summarized with frequency tables by sex (male, female), ERT status (ERT naïve, ERT experienced), and overall if feasible. Unscheduled visits will be included. Clinically significant abnormal values will be collected from investigator assessment on the CRF page.

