11.6. ECG

A summary table of observed and change from baseline values in ECG results will be provided at each scheduled visit for the safety population. A summary table displaying shifts from baseline to worst post-baseline interpretation assessment (including unscheduled assessments as applicable) will be provided by sex (male, female), ERT status (ERT naïve, ERT experienced), and overall if feasible.

A by-subject listing will be provided, including each ECG parameter: heart rate (beats per minute [bpm]), RR interval [msec], PR interval [msec], QRS interval [msec], QT interval mean [msec], QTc (QTcF or QTcB) [msec] and interpretation. QTc = corrected QT interval, QTcF = corrected QT interval with Fridericia's formula, and QTcB = corrected QT interval with Bazett's formula.

12. Reference List

Online source for PedsQL[™] scoring:

http://www.lsebn.nhs.uk/website/X13911/files/20%20scoring_PedsQL_v13[1].pdf

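### The SAP's tables of clinically significant abnormalities have no post-dose limit, so abnormalities already present at entry can be pooled with new ones on drug

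*SAP*

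**What the plan says.** SAP 11.3 lists two categorical laboratory summaries. The first is "The frequencies and percentages of potential clinically significant (PCS) abnormalities at any time", where a PCS value may come from the investigator's assessment or from alert ranges supplied by the sponsor. The second is "Tables displaying shifts from baseline to each assessment time-point in laboratory test values from normal to high or low using normal range", which expressly covers eGFR, urine protein and albumin.

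Three further frequency tables follow, each including unscheduled visits:

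- SAP 11.3: "Clinically significant abnormal assessments for eGFR, urine protein and albumin will be summarized with frequency tables by sex", ERT status and overall.
- SAP 11.4, vital signs: "Clinically significant abnormal results, in which unscheduled visits will be included, will be summarized with the frequency tables".
- SAP 11.5, echo: "Clinically significant abnormal assessments for each parameter will be summarized with frequency tables".

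None of the three gives a start point. SAP 6.5 defines baseline as the last non-missing value on or before the first dose, but removes nothing from a frequency table. SAP 2.2 says that, unless otherwise specified, the analysis uses everything in the database up to lock.

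The ECG section is written differently: "A summary table displaying shifts from baseline to worst post-baseline interpretation assessment". The adverse event tables are also limited, because Protocol 10.1.1 defines a TEAE by onset after the first dose.

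Protocol 8.2.1, criterion 6, requires subjects to "have at least one complication (ie, historical or current laboratory abnormality and/or sign/symptom) of Fabry disease". Its examples include raised LVMi, reduced eGFR or hyperfiltration, and proteinuria or albuminuria.

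**The concern.** Safety is a primary objective in both stages, and the study is uncontrolled, so no comparator arm would show how much of an abnormality count is background disease. The protocol's safety endpoints for laboratory tests, vital signs and echo are changes from baseline. A count that may include screening and Day 1 does not measure change.

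This can mislead in two directions. A subject flagged only before the first capsule raises the count although nothing happened on drug. A subject flagged at entry who then worsens is counted once either way, so the worsening leaves no trace in the table. The parameters in the eGFR/urine and echo tables are among those on which criterion 6 admits subjects, so the risk is greatest there.

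**Working it through.** The plan states no expected frequency for these tables, so there is no figure to reproduce. The check compares the time windows, counts pre-dose assessments, and then shows what pooling does under stated assumptions.

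**1. Time windows side by side**

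| Output | Window in the SAP |
|---|---|
| Laboratory PCS (11.3) | any time, in so many words |
| eGFR/urine protein/albumin (11.3) | none stated |
| Vital signs (11.4) | none stated |
| Echo (11.5) | none stated |
| ECG shift (11.6) | baseline to worst post-baseline |
| TEAEs (11.2; Protocol 10.1.1) | onset after first dose |

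The SAP separates pre-dose from post-dose in the last two rows only. With SAP 2.2 as the default, nothing removes pre-dose values from the first four.

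**2. Pre-dose assessments in the schedule (Protocol Table 3, SAP Table 2)**

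| Domain | Pre-dose | Total | Share |
|---|---|---|---|
| Echo | 2 | 4 | 50% |
| Chemistry/eGFR | 2 | 5 | 40% |
| Urinalysis | 2 | 6 | 33% |
| Haematology | 1 | 3 | 33% |
| Vital signs | 2 | 8 | 25% |

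These are shares of scheduled assessments, not of subjects flagged. They show that pre-dose values exist to be counted in every domain. They do not measure the inflation.

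**3. Effect on subject counts (illustration)**

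N = 20 (Protocol 8.1). Let p0 be the share flagged before dosing and q the rate of new flags among the rest. Both are assumed.

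- Any-time count = N × [p0 + (1 − p0) × q]
- New on drug = N × (1 − p0) × q
- Share of the count already flagged before dosing = p0 / [p0 + (1 − p0) × q]

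For p0 = 25% and q = 10%: 20 × (0.25 + 0.75 × 0.10) = 6.5 any-time; 20 × 0.75 × 0.10 = 1.5 new; 0.25 / 0.325 = 77% already flagged.

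Each cell gives any-time count / new count (share already flagged):

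| p0 | q = 0 | q = 5% | q = 10% | q = 20% |
|---|---|---|---|---|
| 10% | 2.0 / 0 (100%) | 2.9 / 0.9 (69%) | 3.8 / 1.8 (53%) | 5.6 / 3.6 (36%) |
| 25% | 5.0 / 0 (100%) | 5.75 / 0.75 (87%) | 6.5 / 1.5 (77%) | 8.0 / 3.0 (63%) |
| 50% | 10.0 / 0 (100%) | 10.5 / 0.5 (95%) | 11.0 / 1.0 (91%) | 12.0 / 2.0 (83%) |

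With q between 5% and 20%, 36% to 95% of the count was present before dosing. With no new events at all, the table would still show 2 to 10 subjects.

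**4. Would a post-dose limit be enough?**

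Not by itself. In the 25%/10% case, if every entry flag persists after dosing, the post-dose count is again 20 × (0.25 + 0.075) = 6.5. If none persists, it is 1.5. Baseline status has to be shown as well.

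**The case against.** The best counter-argument is that other outputs already separate new from pre-existing abnormalities.

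- Protocol 9.2.2.2.1 requires clinically significant laboratory abnormalities to be recorded as adverse events. Protocol 10.1.1 includes clinically significant changes in other evaluations, and history present at screening only if it worsens. New or worsened investigator-rated findings should therefore reach the TEAE tables. This stands for that route. It does not cover values flagged only by the sponsor's alert ranges, which need not become adverse events.
- The laboratory shift tables name eGFR, urine protein and albumin. Their from-normal wording may be loose: Protocol 11.3.2.2 promises laboratory shift tables without that limit, and SAP 14 declares no change from the protocol. Even so, they use normal ranges rather than PCS thresholds, and they run visit by visit. No shift table is planned for echo or vital signs.
- Baseline can be seen in the by-visit summaries for laboratory tests, vital signs and echo, and in listings with study day. Summary statistics do not show which subjects became abnormal, and listings would need reconstruction by hand.

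A reader might also infer more than the text supports:

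- That the any-time rule governs all these tables. It is written only for laboratory PCS; elsewhere the SAP is silent, which is an omission.
- That many subjects will be flagged before dosing. Criterion 6 needs one complication, accepts historical findings, and lists items such as corneal whorls, hypohidrosis and tinnitus. eGFR below 60 mL/min/1.73 m² at screening is excluded. An abnormal entry value need not be rated clinically significant or fall outside the alert ranges, which the SAP does not give.
- That the SAP presents entry disease as a treatment-emergent finding. It never labels these tables so.

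**Conclusion.** The concern holds in a limited form. As worded, the laboratory PCS table pools pre-dose and on-treatment abnormalities, and the eGFR/urine, vital-sign and echo tables permit the same. Those tables alone cannot distinguish an abnormality brought into the study from one arising on drug.

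The case is strongest for renal and echo parameters, which appear among the entry examples. Echo also has no planned shift table. It is weakest for vital signs, where the entry examples touch little beyond tachycardia or bradycardia.

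The existing safeguards reduce the problem without closing it. Its size is unknown because the documents give no rates of flagged values, before or after dosing; the 36% to 95% range rests wholly on the assumed p0 and q. The tables are descriptive and are not themselves named endpoints, so no test or decision rule is affected. It should still be settled before the shells are final, because these are safety tables in an uncontrolled study with safety as a primary objective.

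**What to change.** In SAP 11.3, 11.4 and 11.5:

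1. Restrict the PCS and clinically significant counts to assessments after the first dose, scheduled and unscheduled.
2. Show status at baseline, as defined in SAP 6.5, in its own column.
3. Report each post-dose abnormality as new, worsened from baseline, or present at baseline without worsening.
4. Keep every subject with at least one post-dose value in the table and state that number as the denominator.

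Counting only subjects who were normal at baseline would not be an adequate substitute. It would drop those who enter abnormal and worsen, who matter in a diseased population.

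The change needs SAP wording, a definition of worsening and revised shells; no new data are collected. The downside is small: extra rows, and small cells with about 20 subjects, especially when split by sex and ERT status.

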5.6. Justification for Proposed Dose and Regimen in Pediatric Subjects with Fabry Disease

Migalastat has not been studied in pediatric subjects under 16 years of age. Although adolescent subjects with Fabry disease 16 to < 18 years of age were included in Phase 3 studies, the number of adolescent subjects included in those studies was limited. Therefore, simulations have been performed (100 subjects per age group) to select doses that match exposure in pediatric patients to exposure observed in adults receiving migalastat HCl 150 mg QOD. Area under the plasma concentration-time curve over the dosing interval (AUC_{0-t}) at steady-state concentration was selected as the target parameter for dose selection in pediatric subjects because existing safety and tolerability data in adults suggest that increased risk is not expected with increases in C_{max} and that changes in minimum observed plasma concentration (C_{min}) are not likely to affect efficacy given there is likely an indirect relationship between plasma concentrations and efficacy. The aim is to achieve AUC values in pediatric subjects that are similar to those in adults with Fabry disease and with normal renal function who were receiving migalastat HCl 150 mg every other day.

The largest biological factor affecting migalastat plasma clearance (CL/F) is renal function. While many adult patients with Fabry disease have reduced renal function (15% and 42% of subjects in Study AT1001-011 with moderate or mild renal impairment, respectively, based on estimated glomerular filtration rate [eGFR]), pediatric patients with Fabry disease have relatively high values for eGFR (mean, 147 mL/min/1.73 m²) (Hopkin, Bissler et al. 2008).

Body weight also explains variability in the pharmacokinetics of migalastat in individuals < 70 kg, with effects on CL/F, volume of distribution in the central compartment (V2/F), volume of distribution in the peripheral compartment (V3/F), and distribution clearance (Q/F). These effects were incorporated into the dose rationale simulations for pediatric subjects by using the range of weights from the Centers for Disease Control and Prevention weight chart (data on file).

Lastly, there is a very small change in CL/F (15%) and V2/F (31%) in the presence of Fabry disease. This effect was accounted for in the simulations, even though these differences result in exposures that are similar to those reported for healthy subjects.

6. **OBJECTIVES AND PURPOSE**

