11.3.2.2. Safety Analyses

Adverse events will be coded using the Medical Dictionary for Regulatory Activities (MedDRA) and summarized by system organ class and preferred term. Summaries will be provided for TEAEs, TEAEs by severity, and TEAEs by relationship to study drug as well as deaths, SAEs, and TEAEs leading to discontinuation of study treatment. Listings will also be provided for SAEs and TEAEs leading to discontinuation of study treatment.

Actual values and changes from baseline for clinical laboratory test results, vital signs, body weight and height, ECG parameters, echocardiogram parameters (other than LVMi) and Tanner stages will be summarized using descriptive statistics. Shift tables will also be provided for clinical laboratory tests and ECG results. Physical examination findings will be summarized by body system.

Concomitant medications will be coded using the World Health Organization (WHO) Drug Dictionary and will be summarized by Anatomical-Therapeutic-Chemical classification.

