12.2. Tanner Stage

A summary table of assessment results in Tanner stage will include Baseline, Month 6 and12/ET visits for the safety population by sex (male, female), ERT status (ERT naïve, ERT experienced). A by-subject listing will be presented for each Tanner stage parameter, including public hair development, breast development, and genital development.

13. Interim Analyses

An interim analysis was conducted on Stage 1 data for PK and safety assessments. The details are provided in a separate Interim SAP.

14. Changes from Analysis Planned in Protocol

No changes are planned from the analyses described in the protocol, amendment 1 (10Sep2018), amendment 2 (31Oct2018), Protocol Amendment 3 (22Apr2019), and Protocol Amendment 4 (13Jun2019).

15. Programming Considerations

All TLFs and statistical analyses will be generated using SAS[®] for Windows, Release 9.4 (SAS[®] Institute Inc., Cary, NC, USA). Computer-generated table, listing and figure output will adhere to the following specifications.

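### SAP 11.3 words the laboratory shift tables, including eGFR and urine protein, so that subjects with an abnormal baseline have no place in them

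*SAP*

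**What the plan says.** SAP 11.3 (Laboratory Evaluations) is the only place that specifies the laboratory shift tables. It asks for "Tables displaying shifts from baseline to each assessment time-point in laboratory test values from normal to high or low using normal range", and the same sentence goes on to name the tests included: "from normal to high or low using normal range including eGFR, urine protein, and albumin". No other SAP text describes a laboratory shift that starts from a high or low value.

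Protocol 11.3.2.2 (Safety Analyses) puts no condition on baseline status: "Shift tables will also be provided for clinical laboratory tests and ECG results". SAP Section 14 then states: "No changes are planned from the analyses described in the protocol". For ECG, SAP 11.6 plans "A summary table displaying shifts from baseline to worst post-baseline interpretation assessment", again with no normal-baseline condition.

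On who enters, Protocol 8.2.1, criterion 6, requires that subjects "have at least one complication (ie, historical or current laboratory abnormality and/or sign/symptom) of Fabry disease, for example". Item g of its list is "reduced eGFR (using the Schwartz formula) for age and sex, or hyperfiltration", with hyperfiltration set at more than 135 mL/min/1.73 m². Item h is proteinuria or albuminuria. Exclusion criterion 1 (Protocol 8.2.2) removes only subjects with eGFR below 60 at screening. Protocol 5.6 notes that "pediatric patients with Fabry disease have relatively high values for eGFR" and cites a mean of 147.

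**The concern.** A shift table is the usual display of how many subjects move between reference-range categories, and from where. If its rows are limited to subjects who start normal, anyone who starts abnormal disappears from it, whether they worsen or improve. The criteria of this trial admit subjects who are abnormal on exactly the tests that the SAP names.

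Two kinds of information are at stake:

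- **Possible harm.** A subject who starts with hyperfiltration and falls below range makes a high-to-low move, which has no cell. Safety is a primary objective of both stages.
- **Possible benefit.** A raised urine protein or a hyperfiltering eGFR that returns to range is high-to-normal, and a reduced eGFR that recovers is low-to-normal. Neither has a cell. These tests are also efficacy endpoints (SAP 3.2.1).

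The narrowing is not declared as a change from the protocol, so a reader of the report would not expect it.

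**Working it through.** The plan gives no figure to reproduce here. There are two checks: a count of cells, and an illustration of how far the effect on eGFR could reach.

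**1. Cells covered.** Three baseline states by three post-baseline states give 3 × 3 = 9 cells.

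| Baseline | Post low | Post normal | Post high |
|---|---|---|---|
| Low | not named | not named | not named |
| Normal | named | not named | named |
| High | not named | not named | not named |

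The SAP wording names 2 cells. One more, normal-to-normal, would follow from the denominator of the normal row. The remaining 9 − 2 − 1 = 6 cells all have an abnormal baseline and are absent.

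**2. Comparison of texts.** The protocol's laboratory shift tables have no baseline condition. The SAP's ECG shift table has none. Only the SAP's laboratory wording has one, and SAP Section 14 declares no change.

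**3. Illustration of reach for eGFR.** Inputs from the documents are the cited paediatric mean of 147 (Protocol 5.6), the hyperfiltration threshold of 135 (Protocol 8.2.1) and about 20 planned subjects (Protocol 8.1). Three assumptions are not in the documents: a normal distribution, an SD of 20 to 40, and a laboratory upper limit near 135.

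Share above 135 = 1 − Φ((135 − mean)/SD), multiplied by 20 subjects:

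- Mean 147, SD 20: Φ(0.60) = 0.726, or 14.5 subjects
- Mean 147, SD 25: Φ(0.48) = 0.684, or 13.7 subjects
- Mean 147, SD 30: Φ(0.40) = 0.655, or 13.1 subjects
- Mean 147, SD 40: Φ(0.30) = 0.618, or 12.4 subjects
- Mean 130 (assumed), SD 20 to 40: 0.401 to 0.450, or 8.0 to 9.0 subjects

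If the laboratory sets no upper limit for eGFR, no subject is high at baseline. Hyperfiltration then removes nobody from the table, and a fall below range is a normal-to-low shift that the SAP does show. The count for hyperfiltration therefore runs from 0 to about 15 of 20, depending on a limit that the documents do not state. Protocol 9.2.5.1 leaves eGFR to the central laboratory's standards.

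**The case against.** The strongest reply is that the phrase is shorthand for an ordinary low/normal/high table. The protocol prescribes no layout and the SAP declares no change, so the documents agree with each other if it is read that way. That may well be the intention. It does not remove the point, because SAP 11.3 is the only text a programmer has for this table, and followed literally it drops subjects.

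The second reply is that other outputs cover the gap. Much of this stands:

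- Summaries of change from baseline at each visit include the minimum and maximum (SAP 6.4.1), so the largest individual eGFR fall at each visit is reported whatever the baseline category.
- SAP 11.3 also plans potentially clinically significant abnormalities at any time, with no condition on baseline, and separate tables of clinically significant eGFR, urine protein and albumin that include unscheduled visits.
- By-subject listings with range flags can be read in full at about 20 subjects.
- Clinically significant laboratory abnormalities must be recorded as adverse events (Protocol 9.2.2.2.1).

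A reader might therefore infer from the shift-table wording that a fall from hyperfiltration to renal impairment would go unseen. The documents do not support that. What these outputs do not supply is a count of subjects by starting and ending category.

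A reader might also infer that the trial selects subjects with abnormal renal tests. It admits them. Items g and h are two of ten listed examples, any one complication is enough, and a historical abnormality counts. Item h may also rest on local laboratory results, so a subject who qualified that way can be normal on the central baseline sample.

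Finally, a full table has limits of its own. A raised urine protein that worsens stays high-to-high, and a low eGFR that falls further stays low-to-low.

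**Conclusion.** The point holds as a defect in the specification of one table. Taken literally, SAP 11.3 gives 2 of 9 shift cells and leaves out every subject with an abnormal baseline on the test concerned. It is narrower than the protocol and than the SAP's own ECG table, without saying so. The cell count rests on the wording alone and needs no assumption.

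The number of subjects affected is not established. It is tempting to conclude that most of the trial, some 12 to 15 of 20, would be missing from the eGFR shift table. That figure needs an assumed SD and an assumed laboratory upper limit near 135. The 135 in the protocol is an eligibility example, not a laboratory reference limit, so the figure should not be cited as a result.

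Severity is minor. The table is descriptive, no test or decision depends on it, and individual values remain visible elsewhere.

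**What to change.** In SAP 11.3, replace the normal-to-high-or-low wording with a full table of baseline category (low, normal, high, missing) by post-baseline category (low, normal, high, missing) at each assessment time point. Use the laboratory's normal range and give each baseline row its own denominator. State the normal range used for eGFR, including whether it has an upper limit.

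Categories built from the protocol's eligibility thresholds (below 60, 60 to 135, above 135) are better avoided. They would place an eGFR that is reduced for age but at least 60 in the middle band, so a fall from 150 to 65 would look like a return to normal.

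The cost is one sentence in the SAP and a standard table shell. No new data are needed, since SAP 11.3 already expects normal ranges and out-of-range flags from the designated laboratory.
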